4 INVESTIGATIONAL PLAN

4.1 Study Design and Duration

The study design schematic is presented in Figure 3.1-1.

Figure 4.1-1: Study Design Schematic

The subjects will be treated in both arms until disease progression, unacceptable toxicity, or subject withdrawal of consent.

This study will consist of three phases: screening, treatment, and follow-up. For a complete list of study required procedures, please refer to [Section 5](#).

Screening Phase:

- Begins by establishing the subject's initial eligibility and signing of the informed consent form (ICF).
- Subject is assessed for complete study eligibility within the required timeframe found in Table 7.1-1.
- A pregnancy test for WOCBP should be documented within 24 hours prior to the start of the first dose of study medication.
- All subjects must have at least 2 distinct lesions as documented by a complete physical examination or imaging studies within 4 weeks prior to randomization. Imaging studies must include a CT scan of the involved disease sites and all known sites of resected disease and brain magnetic resonance (MRI) or CT (brain CT allowable if MRI is contraindicated or if there is no known history of resected brain lesions).

Treatment Phase:

- Following confirmation of the subject's eligibility, the randomization call to the Moffitt Cancer Center Biostatistics Core can be made. The subject is randomly assigned to the Arm A (nivolumab + ipilimumab) or Arm B (nivolumab + ipilimumab + SBRT).
- Within 2 weeks from randomization the subject must receive the first dose of study medication (Day 1 of Week 1)
- On-study laboratory assessments should be drawn within 72 hours prior to dosing
- Adverse event assessments for grade ≥ 2 toxicities should be documented at each clinic visit and WOCBP must have a pregnancy test every four weeks +/- 1 week.
- Treated subjects will be evaluated for recurrence every 12 weeks +/- 7 days
- Patient Reported Outcome (PRO) instruments must be completed after randomization, prior to the dose of study therapy.

Follow-up Phase:

- Begins after 1 year of treatment or when the decision is made to discontinue a subject from study therapy.
- Patient may continue on the study drug under the treatment protocol indefinitely during the follow-up phase.
- After completion of the first two follow-up visits, subjects will be followed every 3 months for survival.
- Subjects who discontinue treatment for reasons other than disease progression will continue to have surveillance assessments (until progression) every 12 weeks \pm 14 days during the first year after randomization, every 12 weeks \pm 21 days during the second year, every 6 months \pm 4 weeks between Year 3 and Year 5 with the last assessment at Year 5.
- Subjects will be followed for drug-related toxicities until these toxicities resolve, return to baseline or are deemed irreversible. All toxicities (\geq grade 2) will be documented for a minimum of 100 days after the last dose of study medication.

The total duration of the study from start of randomization to final analysis of OS is expected to be 84 months (36 months of accrual + 48 months of follow-up), assuming an accrual rate of 17 subjects/year during years 1 – 3.

Stopping criteria: A Safety Monitoring Committee will be formed to evaluate the toxicity of both arms. Interim analysis will be conducted following accrual of initial cohort of patients in the Simon's two stage design to determine whether SBRT introduces excess unanticipated grade 3 or higher toxicities (i.e. radiation pneumonitis, radiation dermatitis, radiation myelitis) prior to expansion of the cohorts.

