6 RADIATION THERAPY

Metastatic lesions with the following distribution are eligible to be treated with SBRT on this protocol:

1 – 4 metastases distinct from the measurable target lesion that will not be irradiated to evaluate responses to the abscopal effect and immunotherapy. Larger lesions are given preference for SBRT to maximize tumor antigen release. The irradiated lesion will not be included in the calculations for measurable disease.

SBRT will be given Week 2 - 3, please see Section 5.5 and 6. SBRT should begin Week 2, and therefore, the radiation planning process should begin as the patient is registered for the study prior to randomization. SBRT for all metastases should be completed within 2 weeks of the first dose of SBRT. Not all metastases need to receive radiation therapy on the same day.

Most commercially available photon producing treatment units are allowed. As such, conventional linear accelerators, specialized linear accelerators with image guidance (e.g., Novalis, Trilogy, Synergy, Artiste, TrueBeam) are allowed. These units can be used with conformal dose delivery or IMRT. Specialized dose painting accelerators (e.g., Cyberknife, Gammaknife or Tomotherapy) are allowed provided they meet the technical specifications of the protocol and are used in a fashion that passes the credentialing required by the protocol. Conventional linear accelerators without add-on IGRT must have some other IGRT capability like CT-on-rails in the treatment room.

IGRT is required for this study. Either 3DCRT or IMRT (including VMAT) are all acceptable planning techniques. Planning techniques may differ for each lesion to be treated provided that the tumor motion is properly accounted for with each technique when the target or targets are in or near the thorax region.

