Surveillance Assessments	Every 12 weeks (\pm 7 days) from first dose of study treatment through 12 months (until distant recurrence)						Clinical exam and/or CT scan of the involved disease sites and all known sites of resected disease and brain MRI (brain CT allowable if MRI is contraindicated or if there is no known history of resected brain lesions). Use same imaging method as was used at screening/baseline.
Study Drug							
Study Treatment	x	x					See Section 5.5.
Outcome Research							
EORTC-QLQ-C30		x					Prior to dosing
EQ5D (optional)		x					
WPAI:GH (optional)		x					
Health Care Resource Utilization (optional)		x					

Table 7.1-7: Follow-Up Procedural Outline

Procedure	Follow-up Visits 1 ^a and 2	Survival, Follow up Visits ^b	Notes
Safety Assessments			
Targeted Physical	x		
Adverse Events	x	x	See Section 6.8 . and Section 8
Laboratory Tests	x		
Pregnancy Test	x		Serum or urine
Review of Concomitant Medication	x		
Outcome Research			
EORTC-QLQ-C30	x		
EQ5D	x	x	
WPAI:GH	x		
Health Care Resource	x		
Efficacy Assessments			
Surveillance Assessment	
Every 12 weeks (\pm 7 days) < 12 months
 
Every 12 weeks (\pm 14 days) > 12 months through 24 months
 
Every 6 months (\pm 4 weeks) > 24 months through and up to Year 5
 
Until distant recurrence. All time points are relative to the first dose of study treatment.
		
Clinical exam and/or CT scan of the involved disease sites and all known sites of resected disease and brain MRI (brain CT allowable if MRI is contraindicated or if there is no known history of resected brain lesions). Use same imaging method as was used at screening/baseline.

Survival status			
Survival status	x	x	Every 3 months, maybe accomplished by visit or phone contact, to include subsequent anti-cancer therapy

^a Follow-up visit 1 (FU1) = 30 days (\pm 7 days) from the last dose, Follow-up visit 2 (FU2) = 84 days (\pm 7 days) from follow-up visit 1.

^b First Survival Follow-up visit 30 days (\pm 7 days) after FU2

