7.4 Efficacy Assessments

Study evaluations will take place in accordance with the flow charts in Section 5. Baseline disease assessments should be performed within 28 days prior to the first dose utilizing CT or MRI. In addition to neck, chest, abdomen, pelvis, and brain, all known sites of disease should be assessed at baseline. Subjects will be evaluated for progression of target lesions or for development of new metastases beginning 12 weeks (+/- 7 days) relative to the first dose of study treatment, and will continue to have surveillance assessment every 12 weeks (+/- 7 days) for the first 12 months. From > 12 months to 24 months after randomization, efficacy assessments should be every 12

weeks (+/- 14 days). From > 24 months until Year 5 after first dose of study treatment, efficacy assessments should be performed every 6 months (+/- 4 weeks).

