9.2.2 Secondary Endpoint(s)

The first secondary endpoint is PFS. PFS will be programmatically determined based on the disease progression date provided by the investigator and is defined as the time between the date of randomization and the date of first progression (local, regional or distant metastasis) or death (whatever the cause), whichever occurs first. (Note: a subject who dies without reported progression will be considered to have progressed on the date of death.) For subjects who remain alive and whose disease has not progressed, PFS will be censored on the date of last evaluable disease assessment.

The second secondary endpoint (OS) is defined as the time between the date of randomization and the date of death. For subjects without documentation of death, OS will be censored on the last

date the subject was known to be alive. OS will be followed continuously while subjects are on the study drug and every 3 months via in-person or phone contact after subjects discontinue the study drug.

To third secondary endpoint to compare the local control of irradiated tumor provided by SBRT in combination with nivolumab versus nivolumab and ipilimumab will be assessed by the local control rate of the irradiated lesion.

The fourth secondary endpoint (to assess the safety and tolerability of nivolumab, SBRT and ipilimumab) will be measured by the incidence of adverse events, serious adverse events, deaths, and laboratory abnormalities.

The fifth secondary endpoint (to evaluate PD-L1 expression as a predictive biomarker) will be measured by the endpoint RFS based on PD-L1 expression level.

The sixth secondary objective (to evaluate HRQoL) will be measured by mean changes from baseline in the EORTC-QLQ-C30 global health status/QoL composite scale and by mean changes from baseline in the remaining EORTC QLQ-C30 scales in all randomized subjects.

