9.3.2.2 Secondary Endpoint Methods

The PFS analyses will be conducted using a two-sided log-rank test stratified by prior immunotherapy exposure in randomized subjects. The hazard ratio and corresponding two-sided 95% CI will be estimated using a Cox proportional hazards model, with treatment group as a single covariate, stratified by the above factors. PFS curves, PFS medians with 95% CIs, and PFS rates at 6, 12, 24 and 36 months with 95% CIs will be estimated using Kaplan-Meier methodology.

The OS analysis will be conducted using a two-sided log-rank test stratified by prior immunotherapy exposure at screening in randomized subjects. The hazard ratio and corresponding two-sided (1-adjusted α)% CI will be estimated using a Cox proportional hazards model, with treatment arm as a single covariate, stratified by the above factors. OS curves, OS medians with 95% CIs and OS rates at 12 and 24 months with 95% CIs will be estimated using Kaplan-Meier methodology.

The local control (LC) of irradiated lesions will be conducted using a two-sided log-rank test stratified by prior immunotherapy exposure at screening in randomized subjects. The hazard ratio and corresponding two-sided (1-adjusted α)% CI will be estimated using a Cox proportional hazards model, with treatment arm as a single covariate, stratified by the above factors. LC curves,

LC medians with 95% CIs and LC rates at 12 and 24 months with 95% CIs will be estimated using Kaplan-Meier methodology.

To evaluate PD-L1 expression as a predictive biomarker, a Cox proportional hazards model will be used to test the interaction between PD-L1 expression (positive vs negative) and treatment arm for the primary and secondary endpoint. Additionally, ORR will be analyzed within each PD-L1 expression subgroup (positive and negative) including log-rank tests and hazard ratios with corresponding confidence intervals. PFS curves and medians will be estimated using Kaplan-Meier methodology. These analyses will be descriptive and not adjusted for multiplicity.

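### PFS runs from randomization in all randomized subjects, but scans run from first dose and only for treated subjects, and the follow-up anchors and windows conflict

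*Combined protocol and SAP*

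**What the plan says.** - **PFS clock.** Section 9.2.2 has PFS "defined as the time between the date of randomization and the date of first progression" (or death). Section 9.3.2.2 states: "The PFS analyses will be conducted using a two-sided log-rank test stratified by prior immunotherapy exposure in randomized subjects". Section 9.1.2 defines that set as everyone randomized, treated or not.
- **Start of treatment.** Section 4.1, for both arms: "Within 2 weeks from randomization the subject must receive the first dose of study medication (Day 1 of Week 1". Section 5.5.1 and Table 7.1-2 repeat the limit.
- **Scan clock on treatment.** The Synopsis (Study Assessments), Tables 7.1-2 to 7.1-6 and Section 7.4 count 12-week intervals from first dose, with a 7-day window either side.
- **Who is scanned.** Section 4.1: "Treated subjects will be evaluated for recurrence every 12 weeks +/- 7 days".
- **Follow-up.** Table 7.1-7: "All time points are relative to the first dose of study treatment". Section 4.1, for subjects who stop drug without progression, refers to scans "during the first year after randomization". Section 7.4 counts year 1 from first dose, then says "From > 12 months to 24 months after randomization", then returns to first dose for the period up to year 5.
- **SBRT preparation, Arm B only.** Section 6: "the radiation planning process should begin as the patient is registered for the study prior to randomization".
- **Censoring.** Section 9.2.2 censors subjects who are alive and progression-free at their latest evaluable assessment. It has no rule for a subject with no assessment after baseline.

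**The concern.** A progression found on imaging is dated at the scan that shows it. If the scan calendar starts later after randomization in one arm, that arm's progressions are recorded later even when the disease behaves identically. The log-rank test uses the order of event times, so a shift of a few days repeated at each scan can look like a treatment effect. Start delay could differ here because the trial is open label (Section 5) and only Arm B needs a radiation plan ready for the week after first dose.

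Two further gaps do not depend on any arm difference. A randomized subject who is never dosed counts in the PFS analysis but has no scan dates. For follow-up, a site can find different anchors and windows depending on which section it reads.

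At stake is the reading of PFS, which Section 9.2.2 lists as the first secondary endpoint and for which a between-arm test and hazard ratio are planned.

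**Working it through.** **The plan's own figure.** The documents give no event count, sample size or power for PFS. The relevant power figure is 85% for the ORR selection rule (Section 9.1.1, 40% vs 17%). Exact calculation: an arm passes both stages with probability 0.9013 at 40% and 0.0978 at 17%. Only B passes: 0.9013 × (1 − 0.0978) = 0.8131. Both pass: 0.9013 × 0.0978 = 0.0881, of which B is chosen by the posterior rule with probability 0.0414. Total: 0.8131 + 0.0414 = 0.8545, which agrees. The rule uses response counts and no event times.

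**The shift.** Let D be days from randomization to first dose, 0 ≤ D ≤ 14. On the PFS clock, scan k falls at D + 84k + W, with W the visit window (−7 to +7). The mean arm shift is Δ = mean D in B − mean D in A, so |Δ| ≤ 14, at most 14/84 = 1/6 of a scan interval. If delays have the same distribution in both arms, nothing is shifted between arms. If scans are counted from randomization, D drops out.

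**Size under no true effect.** Simulation with 25 per arm (the Synopsis gives about 50, 1:1), two-sided unstratified log-rank at 0.05 and 2,000 runs per case. Scans are every 84 days to week 96, then every 182 days, each with the ±7-day window. Assumptions, because the documents give no figures: exponential PFS with median 90, 180 or 365 days; 10% of events are deaths dated exactly; no dropout; B is the later-starting arm. Cells show rejection rate and HR (B vs A).

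| Start delay | Median 90 d | Median 180 d | Median 365 d |
|---|---|---|---|
| Same in both arms (0–14 d) | 6.0%, 1.00 | 5.7%, 0.99 | 4.8%, 1.01 |
| Mean difference 3.5 d | 7.4%, 0.90 | 6.2%, 0.95 | 6.2%, 0.97 |
| Mean difference 7 d (A 0–7, B 7–14) | 10.2%, 0.83 | 7.2%, 0.89 | 6.4%, 0.95 |
| Maximum (all A day 0, all B day 14) | 14.0%, 0.78 | 7.6%, 0.88 | 5.8%, 0.92 |
| Maximum, scans counted from randomization | 4.8%, 0.99 | 5.6%, 1.00 | 5.4%, 1.02 |

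Monte Carlo error is √(0.05 × 0.95/2000) ≈ 0.5 points near 5%. At a 7-day difference, rejections favouring the later arm are 9.6%, 6.0% and 4.2%, against 3.2%, 2.6% and 2.0% with equal delays. The visit window dilutes the effect but does not remove it: for a 3.5-day difference at median 90 days, scans exactly on schedule give 12.0% and HR 0.80, against 7.4% and 0.90 with the window.

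**Progressions found between scans.** Separate runs (24 per arm, 1,500 runs, 5-day difference, medians 3/6/12 months):
- one third of events dated off-scan: 8.1/5.3/4.5%, HR 0.91/0.95/0.98
- half dated off-scan: 6.3/5.8/5.1%, HR 0.94/0.98/1.00

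**Never-dosed subject.** Table 7.1-1 places screening on day −28 to day −1 before randomization. If that is the only assessment, the literal censoring rule gives a PFS time between −28 and −1 days.

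**Follow-up texts side by side.**

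| Place | To 12 months | 12–24 months | Anchor wording |
|---|---|---|---|
| Synopsis | ±14 d (off drug) | ±21 d | first dose |
| Section 4.1 (off drug) | ±14 d | ±21 d | randomization |
| Table 7.1-7 | ±7 d | ±14 d | first dose |
| Section 7.4 | ±7 d | ±14 d | first dose, then randomization for months 12–24 |

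After 24 months all four give 4 weeks (28 days). In year 1, an off-drug scan 10 days late is in window by the first two rows and a deviation by the last two.

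**The case against.** The strongest answer is that an arm difference in start delay is assumed, not documented. Both arms have the same 14-day limit and the same Week 1 drugs. Section 6 has SBRT planning begin before randomization, and SBRT starts the week after first dose, which gives more planning time. This stands: the documents neither show nor exclude a difference. The planning sentence is a recommendation, so it lowers the risk without removing it.

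A reader might infer that any arm difference in start delay produces a false PFS benefit for SBRT, or quote a false-positive rate of about 15–16% with HR about 0.76. The documents do not support either. Those figures need delays of about 3 days in A and 12 in B with almost no spread, a 3-month median, and every progression found at a scheduled scan. Section 3.1 accepts disease measurable by clinical exam, Tables 7.1-2 to 7.1-6 schedule targeted physical exams about every two weeks through week 49, and Section 7.4.3 takes the first date of observed progression by any method. The Synopsis also counts a need for palliative radiation as progression, and deaths carry their own date. With one third of events off-scan, a 9-day difference gives 8.6/5.3/5.1% at medians of 3/6/12 months.

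It can also be said that the randomization wording in Sections 4.1 and 7.4 only marks the period in which an interval applies, without re-anchoring each scan. That reading is possible, but the text does not settle it. The window conflicts affect both arms alike and are not evidence of bias; they are a separate point to reconcile.

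Finally, anchoring scans at randomization would make response scans fall at slightly different drug exposure if delays differ. This carries little weight, because ORR is not read at one fixed exposure.

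**Conclusion.** The mismatch is real and should be corrected. PFS and on-treatment scans start from different dates up to 14 days apart, never-dosed subjects have no scan schedule and no workable censoring date, and the follow-up anchors and windows conflict.

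The bias is conditional. It is zero with equal delays, capped by the 14-day limit, and small unless median PFS is near one 12-week interval. The 7-day row of the table is a reasonable illustration, and its figures shrink further if many progressions are found between scans or are deaths. They rest on assumed medians, delays and exponential PFS.

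The documents do not support a claim that the PFS comparison is biased towards SBRT. Section 1.4.3 treats adequate power for PFS as not feasible, and the ORR decision rule is unaffected. This is an inexpensive improvement to a secondary analysis and does not threaten the trial's main conclusion.

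**What to change.** 1. Count every tumor assessment from randomization, for all randomized subjects, on or off drug and dosed or not, with one window per period. Make the Synopsis, Section 4.1 (Treatment and Follow-up Phases), Tables 7.1-2 to 7.1-7 and Section 7.4 agree.
2. In Section 9.2.2, state that a randomized subject with no post-baseline assessment is censored for PFS on the day of randomization, unless death is recorded.
3. For subjects already scanned on the first-dose clock, report the delay from randomization to first dose by arm and add an interval-censored PFS analysis as a sensitivity analysis.

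Cost: protocol wording, one table and one extra analysis. The third step needs no new data. The downside is that the first scan falls up to 14 days earlier relative to the start of drug.

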Work Productivity and Activity Impairment: General Health (WPAI:GH) is a 6-item questionnaire yielding four different types of scores. The WPAI:GH was created as a patient-reported quantitative assessment of the amount of absenteeism (work time missed), presenteeism (impairment at work), work productivity (overall work impairment/absenteeism plus presenteeism) and daily activity impairment attributable to general health. WPAI:GH outcomes are expressed as impairment percentages, with higher numbers indicating greater impairment and less productivity, ie, worse outcomes. The recall period in all WPAI:GH validation studies is 7 days. The general literature on recall burden suggests that a longer recall period would not be suitable for the type of information being elicited in the WPAI:GH. In theory, a shorter recall period would improve accuracy of WPAI:GH responses, but this has not been tested. Assessment of work productivity will be conducted at each site (or remotely) with the appropriately translated and validated version of the WPAI:GH. All PRO instruments will be administered during on-study, and follow-up phases as outlined in Tables of Section 5.1, respectively, to all randomized subjects. Healthcare resource utilization data (eg, hospitalizations, non-protocol specified medical visits, diagnostics, etc) will be collected for all randomized subjects. The resource utilization capture is specific to hospital admission utilization data and non-protocol specified visits related to study therapy. Resource utilization questions will be asked as outlined in Table of Section 5.1 during screening, on-study, and follow-up phases, respectively.

An **Adverse Event (AE)** is defined as any new untoward medical occurrence or worsening of a preexisting medical condition in a clinical investigation subject administered study drug and that does not necessarily have a causal relationship with this treatment. An AE can therefore be any unfavorable and unintended sign (such as an abnormal laboratory finding), symptom, or disease temporally associated with the use of study drug, whether or not considered related to the study drug.

The causal relationship to study drug is determined by a physician and should be used to assess all adverse events (AE). The causal relationship can be one of the following:

Related: There is a reasonable causal relationship between study drug administration and the AE.

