8.1.1 Serious Adverse Event Collection and Reporting

Sections 5.6.1 and 5.6.2 in the Investigator Brochure (IB) represent the Reference Safety Information to determine expectedness of serious adverse events for expedited reporting. Following the subject's or the legal representative's written consent to participate in the study, all SAEs, whether related or not related to study drug, must be collected, including those thought to be associated with protocol-specified procedures. All SAEs must be collected that occur during the screening period and within 100 days of discontinuation of dosing. If applicable, SAEs must be collected that relate to any later protocol-specified procedure (eg. a follow-up skin biopsy).

The investigator should report any SAE that occurs after these time periods and that is believed to be related to study drug or protocol-specified procedure.

An SAE report should be completed for any event where doubt exists regarding its seriousness.

If the investigator believes that an SAE is not related to study drug, but is potentially related to the conditions of the study (such as withdrawal of previous therapy or a complication of a study procedure), the relationship should be specified in the narrative section of the SAE Report Form.

SAEs, whether related or not related to study drug, and pregnancies must be reported to BMS (or designee) within 24 hours. SAEs must be recorded on the SAE Report Form; pregnancies on a Pregnancy Surveillance Form (electronic or paper forms). The preferred method for SAE data reporting collection is through the eCRF. The paper SAE/pregnancy surveillance forms are only intended as a back-up option when the eCRF system is not functioning. In this case, the paper forms are to be transmitted via email or confirmed facsimile (fax) transmission to:

SAE Email Address: [contact]

SAE [contact]

For studies capturing SAEs/pregnancies through electronic data capture (EDC), electronic submission is the required method for reporting. The paper forms should be used and submitted immediately, only in the event the electronic system is unavailable for transmission. When paper forms are used, the original paper forms are to remain on site.

If only limited information is initially available, follow-up reports are required. (Note: Follow-up SAE reports should include the same investigator term(s) initially reported.)

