8.2.1 Nonserious Adverse Event Collection and Reporting

The collection of new nonserious AE information should begin at initiation of study drug and continue until 100 days from the last dose of study drug. Nonserious AEs should be followed to resolution or stabilization, or reported as SAEs if they become serious. Follow-up is also required for nonserious AEs that cause withholding or discontinuation of study drug and for those present at the end of study treatment as appropriate. All identified nonserious AEs must be recorded and described on the nonserious AE page of the CRF (paper or electronic).

Completion of supplemental CRFs may be requested for AEs and/or laboratory abnormalities that are reported/identified during the course of the study.

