9.3.3 Safety Analyses

Safety analyses will be performed in all treated subjects. Descriptive statistics of safety will be presented using NCI CTCAE version 4.0 by treatment group. All on-study AEs, treatment-related AEs, SAEs, and treatment-related SAEs will be tabulated using worst grade per NCI CTCAE v 4.0 criteria by system organ class and preferred term. On-study lab parameters including hematology, chemistry, liver function, and renal function will be summarized using worst grade NCI CTCAE v 4.0 criteria.

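### Section 4.1 sets a grade 2 threshold for documenting toxicities while Section 8.2.1 requires all nonserious adverse events, so any-grade rates could be incomplete or uneven between sites

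*Combined protocol and SAP*

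**What the plan says.** Section 4.1 sets a grade threshold twice. The treatment-phase list says: "Adverse event assessments for grade ≥ 2 toxicities should be documented at each clinic visit". The follow-up list then covers toxicities (≥ "grade 2) will be documented for a minimum of 100 days after the last dose of study medication".

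Section 8.2.1, which deals with collecting nonserious events, has no threshold: "All identified nonserious AEs must be recorded and described on the nonserious AE page of the CRF". Its time window is stated as "collection of new nonserious AE information should begin at initiation of study drug and continue until 100 days from the last dose". The definition of an adverse event, in the text after Section 7.6, has no grade limit either: "any new untoward medical occurrence or worsening of a preexisting medical condition in a clinical investigation subject administered study drug". For serious events, Section 8.1.1 says that "all SAEs, whether related or not related to study drug, must be collected".

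On the analysis side, Section 9.3.3 says: "All on-study AEs, treatment-related AEs, SAEs, and treatment-related SAEs will be tabulated using worst grade". The fourth secondary endpoint in Section 9.2.2 is the incidence of adverse events, serious adverse events, deaths and laboratory abnormalities. The synopsis adds a chi-square comparison of toxicity between the arms. None of these states a grade floor.

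**The concern.** The protocol gives two rules for the same nonserious grade 1 events over the same period. One stops at grade 2; the other takes everything. The planned tables and the safety endpoint need the second.

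The study is multi-institutional and unblinded, and randomization is stratified by prior immunotherapy, not by site (Section 5.4). A site that works from Section 4.1 and a site that works from Section 8.2.1 would submit different data, and each could point to protocol text in support. A grade 1 clinical event that was never recorded cannot be recovered at analysis. Subjects whose worst event was grade 1 would then drop out of the any-grade rate, and that rate would partly reflect site practice.

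The monthly committee review in Section 8.8 also takes in the frequency of all adverse events, so the same gap could reach it.

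**Working it through.** The point rests on no sample size, power or error-rate figure, so the check is to set the rules side by side.

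| Place | What it governs | Grade floor |
|---|---|---|
| 4.1, treatment phase | Documentation at clinic visits | Grade 2 |
| 4.1, follow-up phase | Documentation for at least 100 days after last dose | Grade 2 |
| 7.3 | Toxicity assessment, continuous on treatment | None |
| 8.1.1 | Collection of serious events | None |
| 8.2.1 | CRF recording of nonserious events, first dose to 100 days after last dose | None |
| 9.2.2, fourth secondary endpoint | Incidence of adverse events | None |
| 9.3.3 | Tables by worst CTCAE grade | None |

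**Same events, same period.** Sections 4.1 and 8.2.1 both run from treatment to 100 days after the last dose. They differ only for events below grade 2.

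**What is exposed.** Serious events are collected whatever their grade. Section 9.3.3 summarizes on-study laboratory parameters by grade as a separate item, so grade 1 laboratory findings do not depend on the adverse event pages. What remains is the nonserious, clinical, grade 1 event.

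**What is not exposed.** Grade 2 or higher and grade 3 or higher rates are the same under either rule. The interim safety look in Section 4.1 concerns grade 3 or higher toxicity.

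**Can the gap be sized?** Not from the documents. The nearest figures are in Section 1.5.4, for single agents in other settings:
- Nivolumab alone: related events of any grade in 72.4% of subjects and grade 3–4 in 14.8%. The difference is 72.4 − 14.8 = 57.6 points.
- Ipilimumab alone: 79% any grade, 21% grade 3/4 and 2% grade 5. The difference is 79 − 21 − 2 = 56 points, or 79 − 21 = 58 if the grade 5 events are already counted in the 21%.

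So about 56 to 58 points of subjects had a worst related event of grade 1 or 2. The grade 1 part lies somewhere between 0 and that figure and cannot be separated. This shows that low-grade events can make up much of an any-grade rate. It does not estimate the loss in this trial.

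**The case against.** The strongest reply is that all-grade collection is already required. Section 8.2.1 is the dedicated collection section and uses *must*. The treatment-phase line in Section 4.1 uses *should*, sits in a phase overview, and does not name the CRF, so it can be read as a minimum for visit notes. Section 4.1 itself sends the reader elsewhere for the full list of procedures. The on-treatment and follow-up schedules in Section 7.1 point to Sections 6.8 and 8 for adverse events, not to Section 4.1. Section 9.3.3 is descriptive, and its higher-grade rows survive under either rule.

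Most of this stands, and it rules out three stronger conclusions that a reader might draw:

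- *Grade 1 events are excluded and any-grade rates will be incomplete.* Section 4.1 does not forbid recording grade 1 events, and Section 8.2.1 requires it. The rates could be incomplete if a site puts Section 4.1 first.
- *A site following Section 4.1 loses every grade 1 event.* Serious events and laboratory grades reach the analysis by other routes.
- *The comparison between arms is biased.* The wording applies to both arms, and the documents show no mechanism that fixes a direction. The synopsis does not say that its chi-square test uses any-grade events.

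The reply does not remove the conflict. The threshold appears twice, the follow-up line uses *will*, and no text gives Section 8.2.1 precedence.

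**Conclusion.** The documents support a finding of conflicting collection rules between Section 4.1 and Section 8.2.1. The consequence is conditional: capture of nonserious clinical grade 1 events could be incomplete or differ by site, and any-grade adverse event rates could then be too low.

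This assumes that at least one site reads Section 4.1 as a limit on what it records. The documents do not show what sites have done. If every site followed Section 8.2.1, nothing is missing by rule.

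The point is minor. No efficacy endpoint or decision rule depends on it. It is still worth correcting, because the missing records could not be rebuilt and the correction is one of wording.

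**What to change.** Reconcile the sections. Remove the grade 2 qualifier from both the treatment-phase and the follow-up lists in Section 4.1, and refer there to Section 8.2.1 as the collection rule. The cost is a wording change and slightly more data entry at any site that has been leaving out grade 1 events.

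If grade 1 events have not been collected uniformly so far, limit the adverse event tables in Section 9.3.3 and the synopsis toxicity comparison to grade 2 or higher, and state the restriction and the reason in the report. That keeps a valid analysis but gives up any-grade rates.
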